### Pre-operative Recommendations

- Ensure subject is informed about the placement of temporary pacing wires during the procedure and any additional associated risks.
- Ensure subject is informed about the potential for the placement of a permanent pacemaker and any additional associated risks.
- Obtain a baseline 12-lead ECG and assess for subject's conduction status
- **Subjects with a pre-existing permanent pacemaker only:** Conduct a full interrogation and AV conduction assessment. Print a copy of the interrogation and save the data on a diskette. Label the diskette with labels provided by Medtronic, including center name, subject ID, date and time of visit/interrogation and type of visit. Retain the printout and diskette in the subject's file for source verification.
  - **Recommended AV conduction assessment:**
    - Conduct an atrial threshold test with a long AV delay (e.g. 350ms) in DDD mode.
    - If the subject's ventricular rhythm doesn't come through within the 350 ms, the subject would be considered dependent on ventricular pacing.

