**C.4.2 Randomization, Sample Size, and Analysis Plan**

Randomization will follow a 1:1 (treatment:control) allocation ratio and be stratified by site and need for revascularization, using a blocked randomization scheme with blocks of randomly varying sizes. The sample size for the mITT population is 1600 subjects.

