Time related safety composite endpoint-incidence estimates will be provided for the two treatment groups at 30 days, 6 months, 12 months, 18 months, 24 months and annually thereafter up to 5 years. The statistical method will be the Bayesian version of a comparison of proportions (with predictions).

\*Refers to VARC-2 definitions

7. Conduction disturbance requiring permanent pacemaker implantation at 30 days, 6 months, 12 months, 18 months, 24 months, and annually thereafter up to 5 years.

The incidence of conduction disturbance requiring permanent pacemaker implantation will be provided at 30 days, 6 months, 12 months, 18 months, 24 months, and annually thereafter up to 5 years, separately for new onset and pre-existing conduction disturbance. The statistical method will be the Bayesian version of a comparison of proportions (with predictions).

8. Change in NYHA class from baseline at 30 days, 6 months, 12 months, 18 months, 24 months, and annually thereafter up to 5 years.

NYHA classifications will be summarized with frequencies and percentages at baseline, 30 days, 6 months, 12 months, 18 months, 24 months, and annually through five years. Change in NYHA classification from baseline will be summarized both with frequencies and percentages and as continuous data at 30 days, 6 months, 12 months, 18 months, 24 months and annually through five years.

For each subject with paired data, the number of classes changed from baseline (-3, -2, -1, 0, 1, 2, or 3) will be calculated at 30 days, 6 months, 12 months, 18 months, 24 months, and annually thereafter up to 5 years. For each treatment group, a Bayesian version of a paired t-test will be performed to evaluate change from baseline at 30 days, 6 months, 12 months, 18 months, 24 months, and annually through five years. The endpoint will be evaluated between groups using a Bayesian version of a t-test.

9. Change in distance walked during 6-minute walk test (6MWT) from baseline to 30 days, baseline to 12 months, and baseline to 24 months.

All subjects who are able to perform the six-minute walk evaluation at the time of the follow-up visit will be included in the analysis.

The endpoint will be evaluated using a Bayesian version of a t-test.

10. Ratio of days alive out of hospital versus total days alive assessed at 12 months and 24 months follow-up.

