Index procedure-related MAE events will be summarized and event rates will be provided at 30 days. The numerator will be the number of procedure-related MAE events experienced by the end of the 30-day follow-up visit, and the denominator will be the number of subjects evaluated at the 30-day follow-up visit (or a later follow-up) plus the number of subjects not evaluated but who experienced a procedure-related MAE event prior to the end of the follow-up visit window.

Additionally, the percentage of subjects with a procedure-related MAE will be calculated in the same way, but allowing no more than one MAE per subject. The endpoint is descriptive and no statistical hypothesis test will be performed.

18. Length of index procedure hospital stay

The length of TAVI or SAVR hospital stay will be summarized for all subjects undergoing a study procedure.

The endpoint will be evaluated between groups using a Bayesian version of a t-test.

19. Presence of atrial fibrillation at post-procedure, discharge, 30 days, 6 months, 12 months, 18 months, 24 months, and annually thereafter up to 5 years.

The statistical method will be the Bayesian version of a comparison of proportions (with predictions).

The following secondary endpoints will be assessed for the TAVI cohort subjects only:

20. Device success defined as follows:

- Absence of procedural mortality AND
- Correct positioning of a single prosthetic heart valve into the proper anatomical location AND
- Intended performance of the prosthetic heart valve (no prosthesis-patient mismatch and mean aortic valve gradient <20 mmHg or peak velocity <3 m/s, AND no moderate or severe prosthetic valve regurgitation\*)
  - assessed acutely in a resting state, either within 24-48 hours after the index procedure or before hospital discharge

\*Refers to VARC-2 definitions

Device success, as defined above, will be calculated for all subjects undergoing the TAVI procedure.

The endpoint is descriptive and no statistical hypothesis test will be performed.

21. Procedural success, defined as device success and absence of in-hospital MACCE.
- Procedural success, as defined above, will be calculated for all randomized subjects undergoing the TAVI procedure.
- The endpoint is descriptive and no statistical hypothesis test will be performed.
22. Evidence of prosthetic valve dysfunction at 30 days, 6 months, 12 months, 24 months, and annually thereafter up to 5 years.

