### C.11.3 Discrete (Dichotomous) Data: Bayesian Comparison of Proportions (with Predictions)

The analysis above under “Bayesian Version of a Comparison of Proportions” applies only to subjects with observed data at the time point of interest (eg, the 24-month visit). A modification is required in order to take into account subjects with partial follow-up, as will be the case if non-inferiority is demonstrated for the primary objective at the interim analysis time point.

The modeling is analogous to the predictions in the Primary Objective. Subjects without outcome data for the time point of interest  $T_0$  will be considered to be in intermediate states that are analogous to those used in the primary objective. If  $T_0 = 24$  months, subjects without 24-month outcome data will be considered to be in one of 26 states (13 for each treatment group). The 13 states are:

- no interim data
- E or P or N at 1 month, no subsequent data
- E or P or N at 6 months, no subsequent data
- E or P or N at 12 months, no subsequent data
- E or P or N at 18 months, no subsequent data

If  $T_0$  is later (eg, 3 years), there is one more set of 3 interim states (E or P or N at 24 months). If the time point of interest is sooner (eg, 12 months), only the first few bullets above (measured at time points prior to  $T_0$ ) would apply.

As with the primary objective analysis, subjects in the "E" state at interim time points can be imputed to be "E" at  $T_0$ , with certainty. For each of the remaining interim states (separately by treatment group), the probability of becoming an "E" at 24 months is modeled via a Beta(1,1) prior distribution which is updated to a Beta(1+X, 1+Y) distribution, based on the number X and Y of subjects who went on from that state to become 24-month "E" and "N" subjects, respectively.

Predicting 2-year outcomes for each of these states, and combining with the data from subjects with known 2-year outcomes, a posterior probability of non-inferiority (or superiority) is calculated; it is based on observed 2-year data and also a predictive model that employs interim outcomes and the relationship between those interim outcomes and their corresponding final outcomes that is learned during the current trial.

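### The atrial fibrillation endpoint compares AF prevalence at each visit regardless of baseline rhythm, so it cannot separate new AF after the procedure from AF already present

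*Combined protocol and SAP*

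**What the plan says.** SAP version 6.0 (based on CIP Version 12.0), section C.10, item 19 reads "Presence of atrial fibrillation at post-procedure, discharge, 30 days, 6 months", and goes on to 12, 18 and 24 months and then yearly to 5 years. The method is the Bayesian comparison of proportions with predictions. Section C.11.3 puts Beta(1,1) priors on the two arm proportions and on the transition probabilities, and has no covariate. Nothing in item 19 excludes subjects with prior AF, separates new from existing AF, or adjusts for baseline rhythm.

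The same list does draw this distinction for another rhythm-related outcome. Item 7 gives permanent pacemaker implantation for conduction disturbance "separately for new onset and pre-existing conduction disturbance". Ordered objective 18 in C.12.1 concerns new pacemaker implants.

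On baseline recording, the pacing guidelines (R.13, Pre-operative Recommendations) advise sites to "Obtain a baseline 12-lead ECG and assess for subject's conduction status". The ECG submission appendix (R.8, Labeling) gives screening as an example of an ECG interval. The echocardiography guidelines (R.7, section 4) have an averaging rule for patients not in sinus rhythm, so the plan does not assume that everyone enters in sinus rhythm.

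AF is not among the 18 ordered objectives in C.12.1. Section C.12 says that secondary objectives outside that list will not support labeling claims.

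**The concern.** A subject who is in AF before treatment and still in AF at a visit counts as having the endpoint, whichever arm they are in. Such a subject says nothing about whether the procedure brought on AF, yet adds to both arm rates. The reported figure is therefore part new AF and part rhythm at entry, and the plan gives no way to tell the parts apart.

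At stake is what a reader can conclude about AF after TAVI or surgery. A moderate difference in new AF could be diluted until it looks small. If one strategy also changes how often existing AF persists, the comparison would blend two different effects.

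**Working it through.** **The plan's own figures.** The documents state no AF rate, effect size or power, so there is nothing to reproduce for this endpoint. The trial size is 1600 mITT subjects, and C.4.2 states "Randomization will follow a 1:1 (treatment:control) allocation ratio", which gives 800 per arm.

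**Model.** Let b be the share in AF before treatment (equal between arms in expectation under randomization), q the share of those still in AF at the visit, and i the new-onset rate among the rest. Deaths and missed visits are ignored. Then

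presence = b·q + (1 − b)·i

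With the same q in both arms, the b·q term cancels from the difference:

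difference (SAVR − TAVI) = (1 − b)·(i_SAVR − i_TAVI)

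The shrinkage factor is (1 − b) for any onset rates and any common q. The ratio also depends on q.

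**Size, assuming onset of 10% TAVI and 20% SAVR, q = 1.** Among subjects free of AF at baseline, the difference is 10 points and the ratio 0.50. As presence:

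| b | TAVI | SAVR | Difference | Ratio |
|---|---|---|---|---|
| 10% | 0.10 + 0.90×0.10 = 0.19 | 0.10 + 0.90×0.20 = 0.28 | 9 points | 0.68 |
| 20% | 0.28 | 0.36 | 8 points | 0.78 |
| 30% | 0.37 | 0.44 | 7 points | 0.84 |
| 40% | 0.46 | 0.52 | 6 points | 0.88 |

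With q = 0.7 in both arms the differences are the same and the ratios are 0.64, 0.73, 0.80 and 0.85.

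**Unequal persistence, same onset rates, b = 30%.**

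| q TAVI | q SAVR | TAVI | SAVR | Difference |
|---|---|---|---|---|
| 1.0 | 1.0 | 0.37 | 0.44 | 7 points |
| 1.0 | 0.8 | 0.37 | 0.38 | 1 point |
| 1.0 | 0.6 | 0.37 | 0.32 | −5 points |
| 0.8 | 1.0 | 0.31 | 0.44 | 13 points |

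The new-onset difference is 10 points in every row.

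**Power, assuming onset of 10% versus 15%, q = 1.** The test is the usual two-proportion test at one-sided 0.025. That level is an assumption for this endpoint; it matches the 0.975 threshold that C.12.1 uses for superiority. With p̄ the mean of the two rates,

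power = Φ{ [√n·|d| − 1.96·√(2p̄(1 − p̄))] / √(p_T(1 − p_T) + p_C(1 − p_C)) }

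At b = 30%:

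- Presence: 0.30 + 0.70×0.10 = 0.370 versus 0.30 + 0.70×0.15 = 0.405, d = 0.035, n = 800. This gives (0.990 − 1.350)/0.689 = −0.52, power 0.30.
- New onset: 0.10 versus 0.15, d = 0.05, n = 800×0.70 = 560. This gives (1.183 − 0.917)/0.466 = 0.57, power 0.72.

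| b | Power, presence (800 per arm) | Power, new onset (n per arm) |
|---|---|---|
| 10% | 0.595 | 0.819 (720) |
| 20% | 0.415 | 0.772 (640) |
| 30% | 0.300 | 0.716 (560) |
| 40% | 0.224 | 0.649 (480) |

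In these scenarios the new-onset comparison has more power despite its smaller denominator.

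**A large effect.** With assumed onset of 10% versus 35% and b = 25%, presence is 0.325 versus 0.5125: 18.75 points and a ratio of 0.63, against 25 points and 0.29 for new onset. The standard error at 800 per arm is √[(0.325×0.675 + 0.5125×0.4875)/800] = 0.0242, so the diluted difference is still about 7.7 standard errors.

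**The case against.** The strongest reply is that the plan asks about the presence of AF and measures it. Prevalence by visit is a coherent outcome, and randomization makes the comparison fair. This stands. A reader might infer that the endpoint is confounded or invalid, and the documents do not support that. The limitation is in what the result can be taken to mean, and in precision for new AF.

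A reader might also infer that the endpoint always pulls toward no difference. It does so only if pre-existing AF persists equally in both arms; the unequal-persistence table shows the difference widening or reversing. Nor can one say that the rate mostly reflects who was enrolled. In the large-effect example, baseline AF makes up 0.25/0.325 = 77% of TAVI events but only 0.25/0.5125 = 49% of SAVR events. In that example the qualitative conclusion also survives dilution.

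Item 7 is only a partial precedent. It counts an intervention, classified by the underlying disturbance, and it does not make the pre-existing group descriptive or restrict the comparison to subjects free of disturbance at entry. It does show that the plan considers the split worth making.

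The R.13 baseline ECG is a recommendation about conduction status. The screening interval in R.8 is better support for a recorded baseline rhythm. Collection of AF history is not shown in the available text.

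Finally, section O.2 (Definitions of Terms), to which C.14.2 refers, was not available for review. A definition there could narrow the endpoint, although nothing in the available text does so.

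**Conclusion.** The point holds as a limit on interpretation and precision. As written in C.10, item 19 cannot separate new AF after the procedure from AF present before it. With equal persistence, the absolute difference loses a share equal to baseline AF prevalence: 10% to 40% of its size for prevalence of 10% to 40%. With unequal persistence the direction is not predictable.

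The shrinkage factor is algebra and needs no rate assumption beyond equal persistence and balanced baseline AF. The ratios and power figures rest entirely on assumed onset rates and baseline prevalence. Because AF is outside the labeling hierarchy, a reader should not infer that a claim or the trial's error control is at risk. This is a worthwhile refinement of low severity.

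**What to change.** In C.10 item 19, add a between-arm comparison of new-onset AF among subjects with no AF on the screening or baseline ECG, supplemented by AF history where it is recorded. Report AF results separately by baseline AF status, in line with the new-onset and pre-existing split in item 7. Keep overall AF prevalence by visit as a supplementary summary. State which ECG defines baseline rhythm and how a subject with no baseline ECG is classified. If section O.2 already restricts the endpoint, a cross-reference in item 19 would be enough.

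The text change is short, and sample size, primary analysis and multiplicity plan are unaffected. The statistical cost is a smaller denominator for the new-onset comparison, for example 560 instead of 800 per arm at 30% baseline AF. The sponsor should first confirm that baseline rhythm is captured in the database for both arms.

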## C.5 Predictions

Outcomes at 24-month are binary and are denoted "E" (for having experienced an Event) or "N" (for not having experienced an event). Predicted values of 24-month outcomes for those subjects who have not yet yielded 24-month outcomes will be based on intermediate outcomes observed at 1 month, 6 months, 12 months, and 18 months. These intermediate outcomes are:

[figure not shown]
- "E" -- subject has had a known primary event (death or disabling stroke) at the time point in question
- "P" -- subject is known to have had a "possible primary event" at the time point in question. "Possible primary events" are adverse events that may later be determined to be Disabling Strokes. This determination takes 90 days, by definition. For example, a subject may have a stroke at month 5 which cannot be known to be a Disabling Stroke until Month 8. At Month 6, such a subject is in the "P" state.
- "N" -- subject has not had a primary event or a "possible primary event" at the time point in question.

Subjects without 24-month outcome data will thus be considered to be in one of 26 states (13 for each treatment group). The 13 states are:

- no interim data
- E or P or N at 1 month, no subsequent data
- E or P or N at 6 months, no subsequent data
- E or P or N at 12 months, no subsequent data
- E or P or N at 18 months, no subsequent data

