Additionally, incidence of major vascular complications and incidence of major or life-threatening bleeding events at 30 days or hospital discharge, whichever is longer, will also be compared using the Bayesian version of a comparison of proportions.

4. Incidence of Early safety at 30 days defined as a composite of:

- All-cause mortality
- All stroke (disabling and non-disabling)
- Life-threatening bleeding
- Acute kidney injury—Stage 2 or 3 (including renal replacement therapy)
- Coronary artery obstruction requiring intervention
- Major vascular complication
- Valve-related dysfunction requiring repeat procedure (BAV, TAVI, or SAVR)
- All-cause death

Early safety composite endpoint-incidence estimates will be provided for the two treatment groups at 30 days. The statistical method will be the Bayesian version of a comparison of proportions.

5. Incidence of Clinical Efficacy (after 30 days) at 6 months, 12 months, 18 months, 24 months and annually thereafter up to 5 years. Clinical efficacy defined as a composite of:
- All-cause mortality
  - All stroke (disabling and non-disabling)
  - Requiring hospitalizations for valve-related symptoms or worsening congestive heart failure
  - NYHA class III or IV
  - Valve-related dysfunction (mean aortic valve gradient  $\geq 20$  mmHg, EOA  $\leq 0.9$ - $1.1$  cm^2 and/or DVI  $< 0.35$  m/s, AND/OR moderate or severe prosthetic valve regurgitation\*)

Clinical efficacy estimates will be provided for the two treatment groups at 6 months, 12 months, 18 months, 24 months and annually thereafter up to 5 years. The statistical method will be the Bayesian version of a comparison of proportions (with predictions).

\*Refers to VARC-2 definitions

6. Incidence of Time-Related Safety at 30 days, 6 months, 12 months, 18 months, 24 months and annually thereafter up to 5 years. Time-Related Safety defined as a composite of:
- Structural valve deterioration:
    - Valve-related dysfunction (mean aortic valve gradient  $\geq 20$  mmHg, EOA  $\leq 0.9$ - $1.1$  cm^2 and/or DVI  $< 0.35$  m/s, AND/OR moderate or severe prosthetic valve regurgitation\*)
    - Requiring repeat procedure (TAVI or SAVR)
  - Prosthetic valve endocarditis
  - Prosthetic valve thrombosis
  - Thromboembolic events (e.g. stroke)
  - VARC bleeding, unless clearly unrelated to valve therapy (e.g. trauma)

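### Atrial fibrillation at a visit can resolve, but the prediction method assigned to it (secondary endpoint 19) carries AF at the last observed visit forward as certain

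*Combined protocol and SAP*

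**What the plan says.** In SAP version 6.0 (written for CIP Version 12.0), section C.10, secondary endpoint 19 is "Presence of atrial fibrillation at post-procedure, discharge, 30 days, 6 months, 12 months", continuing through 18 and 24 months and then yearly to 5 years. Its method line reads "The statistical method will be the Bayesian version of a comparison of proportions (with predictions", which is the method of C.11.3.

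Under C.11.3 a subject without an outcome at the target time T0 is placed in the last observed state, for example "E or P or N at 18 months, no subsequent data". The rule for the event state is that "subjects in the 'E' state at interim time points can be imputed to be 'E' at" T0, with certainty. Only the other states are estimated: "For each of the remaining interim states (separately by treatment group), the probability of becoming an 'E' at 24 months is modeled via a Beta(1,1". Counts of how many subjects went from that state to E or to N then update this starting distribution. The section says prediction is needed when follow-up is partial, "as will be the case if non-inferiority is demonstrated for the primary objective at the interim analysis time point".

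The method is borrowed from the primary endpoint. There (C.5), E means "subject has had a known primary event (death or disabling stroke) at the time point in question".

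**The concern.** Having had a death or disabling stroke cannot be undone, so fixing the E-to-E probability at 1 is correct for the primary endpoint. Presence of AF at a visit can be undone, and C.11.3 has no route from E to N. A subject in AF at 12 months who is seen out of AF at 24 months counts as N. A subject in the same 12-month state who has not yet reached 24 months counts as E with probability 1. The reported proportion mixes the two.

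Appendix G.5 defends prediction partly on the ground that its quality is learned within the trial. For AF persistence nothing is learned, although the subjects with 24-month data carry that information.

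Reading endpoint 19 as visit status is the natural reading. Neighbouring endpoints speak of incidence or of the number of subjects with an event. This one speaks of presence, lists post-procedure and discharge as separate times, and is not limited to new-onset AF. At stake are the 24-month AF proportions, and possibly their comparison between arms, in an Early Win report.

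**Working it through.** **1. Reproduce the plan's own counts.** Inputs: accrual of 576 over months 1-21, then 45 per month (30 slow, 60 fast), from C.7.3; Early Win 12 months after the 1400th mITT subject, from C.7.3.1; 6% dropout over 24 months, from C.7.1.

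Subjects with 24 months of follow-up at the Early Win = (1400 - 12 x rate) x 0.94.

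- Expected: 860 x 0.94 = 808.4 (Table 6: 808)
- Slow: 1040 x 0.94 = 977.6 (Table 6: 978)
- Fast: 680 x 0.94 = 639.2 (Table 6: 639)

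The figures reproduce.

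**2. Share without 24-month status, N = 1600.**

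- Expected: 1 - 808/1600 = 49.5%
- Slow: 1 - 978/1600 = 38.9%
- Fast: 1 - 639/1600 = 60.1%

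**3. Where the last observed state lies.** Under expected accrual the 1400th subject enters at month 21 + (1400 - 576)/45 = 39.31, so the Early Win falls at month 51.31. The 1600th enters at 21 + (1600 - 576)/45 = 43.76 and so has about 7.5 months of follow-up. Before dropout the groups are:

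- 24 months or more: 860
- 18 to 24 months: 6 x 45 = 270
- 12 to 18 months: 270
- under 12 months: 1600 - 1400 = 200, all past 6 months

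The imputed subjects therefore have last states at 18, 12 and 6 months. A 1-month last state needs a loss between months 1 and 6: 0.06 x 5/24 = 1.25% of subjects. Under slow accrual the newest subject has 5.33 months, which adds only about (6 - 5.33) x 30 = 20 subjects.

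**4. Size of the overstatement.** Overstatement = s x p x r, where s is the share missing, p the AF prevalence at the last visit and r the probability of being out of AF by T0. The documents give neither p nor r. With p = 15% assumed, in percentage points:

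| Look | s | r = 10% | r = 30% | r = 60% |
|---|---|---|---|---|
| Early Win, expected accrual | 0.495 | 0.74 | 2.23 | 4.46 |
| Early Win, slow | 0.389 | 0.58 | 1.75 | 3.50 |
| Early Win, fast | 0.601 | 0.90 | 2.70 | 5.41 |
| Final look, losses only | 0.06 | 0.09 | 0.27 | 0.54 |

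The overstatement is zero only if AF never resolves.

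**5. Between-arm effect.** The distortion is s x (p x r in one arm minus p x r in the other), and is zero when the products are equal. If prevalence were 20% against 10% with common reversion of 30-60% (assumed), it would be 0.495 x 0.10 x 0.3 to 0.6 = 1.5 to 3.0 points.

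**6. Check by simulation, all rates assumed.** Setup: 800 per arm, 404 observed at 24 months, AF 30% at the last visit, 50% persistence, 5% new AF. True prevalence was 18.5%. The certain-E rule gave 26.0%. A Beta(1,1) transition for E, updated within arm, gave 18.6%. The formula predicts 0.495 x 0.30 x 0.50 = 7.4 points of bias; the simulation shows 26.0 - 18.5 = 7.5.

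**The case against.** A reader might infer that AF seen soon after the procedure is carried to 24 months, so that the arm with more transient early AF is penalised. The documents do not support that. Post-procedure and discharge are not states in C.11.3, and only the last observed state counts: AF at 30 days that is gone at 6 months is classed as N. With a 1-month last state in about 1.25% of subjects, this route contributes 0.0125 x 15% x 30-60% = 0.06 to 0.11 points under the same assumptions. What remains is AF still present at 6, 12 or 18 months. It may revert less often than early AF, which points to the lower end of the table.

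A reader might also infer that the composites are wrong. Endpoint 5 includes "NYHA class III or IV" and valve dysfunction, but it is headed as an incidence. If that means cumulative, a permanent event state is coherent, so this is a point to check and not an error shown.

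Three further limits stand:

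- Observed T0 status is always used when available, so the final look is barely affected.
- AF is not among the 18 labeling objectives in C.12.1, nor in the C.9.2 list for inferential analysis.
- The body of the clinical investigation plan, including the O.2 definitions that the SAP cites, was not in the text available here. A cumulative AF definition there would make the rule coherent, though the SAP wording would still read as visit status.

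**Conclusion.** On the SAP's wording, endpoint 19 and its assigned method do not fit: a reversible visit status is treated as permanent for everyone whose outcome must be predicted. The direction is certain if any AF resolves; the size is not, because the documents give no AF rates. With 15% prevalence assumed and expected accrual, the 24-month overstatement at an Early Win is about 0.7 points at 10% reversion and 2 to 4.5 points at 30-60%. At the final look it is about 0.1 to 0.5 points.

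A spurious treatment difference follows only if prevalence or reversion differs between arms, which the documents do not establish. The primary endpoint, its error control and the labeling claims are untouched. The point deserves correction because a secondary result would otherwise depend partly on who has incomplete follow-up, and the repair is cheap.

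**What to change.** Add a sentence to C.11.3: for endpoints defined as status at a visit, each interim E state receives its own Beta(1,1) transition to E at T0, updated within arm, as already done for P and N. Alternatively, analyse such endpoints on observed data only by C.11.1. Apply this to endpoint 19, and to endpoint 22 (prosthetic valve dysfunction) if that is meant as status at the visit. Keep the certain-E rule for cumulative endpoints, and state for endpoint 5 whether its components are cumulative.

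If endpoint 19 is meant as cumulative ever-AF, reword it so; the existing rule then applies.

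The cost is SAP wording and a small programming change. No new data are needed, and the simulations of the primary endpoint are unaffected.
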